9.2 Number of Centres

This is a single centre study, which will be conducted in the John Farman Intensive Care Unit at Addenbrooke's Hospital in Cambridge. The JFICU has 20 beds and admits up to 1200 patients per year.

9.3 Number of Subjects

We plan to include 600 patients in this study. This number is based on the estimated number of patients admitted to the John Farman Intensive Care Unit during the six-month study period.

9.4 Participants Study duration

The participants' study duration will be dependent on the duration of their admission to the John Farman Intensive Care Unit. In January 2015 the mean length of stay was 7.19 days (standard deviation \pm 8.94 days) and the median was 3.4 days (range 0.2 to 47.2 days). The duration of the whole study is six months.

9.5 Study objectives

9.5.1 Primary objective

To determine the rates of carriage, infection and transmission of MDRO in the John Farman Intensive Care unit at Addenbrooke's Hospital using bacterial whole-genome sequencing.

9.5.2 Secondary objectives

7.5.2.1. To compare standard epidemiological investigation / typing with whole-genome sequencing in the investigation of suspected MDRO outbreaks

9.5.3. To conduct a health economic evaluation of standard epidemiological investigation / typing with whole-genome sequencing in the investigation of suspected MDRO outbreaks

9.6 Study Outcome Measures

9.6.1 Primary outcome measures

The primary outcome measures of the study will be:

- Number of patients colonised with MDRO
- Number of patients with clinical evidence of infection with MDRO
- Number of transmission events of MDRO

9.6.2 Secondary outcome measure

The secondary outcome measures of the study will be:

- Risk factors for colonisation / infection with MDRO
- Outcome of patients colonised / infected with MDRO
- Cost-effectiveness of whole-genome sequencing versus standard epidemiological investigation / typing for suspected MDRO outbreaks

10 Selection and withdrawal of subjects

10.1 Inclusion Criteria

To be included in the study the patient must be:

- Aged 18 years old or older
- Male or female
- Admitted to the John Farman Intensive Care Unit during the study period

10.2 Exclusion Criteria

The presence of any of the following will preclude patient inclusion:

- Age less than 18 years
- Does not fulfil study inclusion criteria

10.3 Treatment

This is a prospective observational cohort study for surveillance of MDRO in intensive care. Participants will receive routine clinical care including antibiotics to treat infections as clinically indicated. There are no study specific interventions or treatments.

10.4 Subject withdrawal criteria

All adult patients admitted to the John Farman Intensive Care Unit during the study period will be enrolled into the study. As this is a surveillance study for healthcare-associated infections, written informed consent from individual participants will not be required prior to study entry. Information about the study will be displayed on posters on the ward and

patients who wish to withdraw from the study may do so by informing the staff on the intensive care unit. This will not affect the treatment that they receive.

11 Procedures and assessments

11.1 Screening

11.1.1 Subject identification

All patients admitted to the John Farman ICU during the study period will be eligible for inclusion in the study

11.1.2 Consent procedures

As this is a surveillance study for MDRO / healthcare-associated infections, written informed consent from individual participants will not be required prior to study entry.

11.1.3 Subject registration

All study participants will be assigned a unique anonymised identification code, which will be used in the case record form, laboratory request forms and the study database.

11.2 Baseline assessments

11.2.1 Screening for multidrug-resistant organisms (research specimens)

Participants will be screened for MDRO on admission to the John Farman Intensive Care Unit. All specimens will be assigned a unique anonymised identification number prior to transfer to the research laboratory the Department of Medicine for processing.

Specimens will be cultured on selective media for the following target organisms:

- Vancomycin-resistant enterococci (VRE)
- Extended spectrum beta-lactamase producing Enterobacteriaceae (ESBL)
- Carbapenem-resistant organisms (CRO)

Samples that are positive for suspected target organisms will undergo identification using MALDI TOF MS and antimicrobial susceptibility testing using the Vitek-2 system.

Isolates that are confirmed to be target organisms will undergo DNA extraction and storage at -80 $^\circ\text{C}.$

DNA extracts will be transferred in batches to the Wellcome Trust Sanger Institute for DNA library preparation and high-throughput microbial whole-genome sequencing.

11.2.2 Clinical diagnostic specimens

Clinical diagnostic specimens will be collected as clinically indicated and processed in the diagnostic microbiology laboratory at Addenbrooke's hospital according to routine clinical practice.

Samples that are positive for the target organisms will be identified by the laboratory information system and retrieved from the diagnostic microbiology laboratory on weekdays for further processing as detailed above.

11.2.3 Clinical data collection

Clinical and laboratory data will be collected on each patient by a research nurse who is part of the ICU clinical care team and entered into a case record form.

Clinical data collection will be performed on admission to ICU, on discharge from ICU and weekly during the ICU admission if the duration of admission is 7 days or longer.

Data will be entered into a secure electronic database located on the Addenbrooke's hospital server. Data will be anonymised as soon as it is practical to do so.

11.3 Follow-up assessments

11.3.1 Screening for multidrug-resistant organisms (MDRO) (research specimens) Participants will be screened for MDRO on discharge from ICU, and weekly during their ICU admission if the duration of admission is 7 days or longer.

All specimens will be assigned a unique anonymised identification number prior to transfer to the research laboratory the Department of Medicine for processing.

Specimens will be cultured on selective media for the following target organisms:

- Vancomycin-resistant enterococci (VRE)
- Extended spectrum beta-lactamase producing Enterobacteriaceae (ESBL)
- Carbapenem-resistant organisms (CRO)

Samples that are positive for suspected target organisms will undergo identification using MALDI TOF MS and antimicrobial susceptibility using Vitek-2 system.

Isolates that are confirmed to be target organisms will undergo DNA extraction and storage at -80 °C.

DNA extracts will be transferred in batches to the Wellcome Trust Sanger Institute for DNA library preparation and high-throughput microbial whole-genome sequencing.

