11.5 Sampling schedule

11.5.1 Clinical data collection and screening for MDRO (research specimens) Screening specimens will be collected on admission, on discharge, and weekly in patients admitted for ≥7 days according the following schedule:

Study specimens	Admission	Discharge	Follow-up (weekly)
Clinical data collection	\checkmark	\checkmark	\checkmark
Stool sample / rectal swab*	\checkmark	\checkmark	\checkmark
Urine	\checkmark	\checkmark	\checkmark
Sputum or tracheal aspirate	\checkmark	\checkmark	\checkmark
Wound swab (if applicable)	\checkmark	\checkmark	\checkmark

*A rectal swab will only be collected if a stool sample is unavailable. This is standard clinical practice for screening for carbapenem-resistant organisms, as recommended by the Public Health England guidelines.

Specimens will be sent to the research laboratory in the Department of Medicine for processing Monday to Friday.

Samples that are collected at the weekend will be stored at 4° C in a refrigerator on the ICU and processed the following Monday.

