13.1 Primary outcome measures

The primary outcome measures are:

- Number of patients colonised with MDRO during the study period
- Number of patients with clinical evidence of infection with MDRO during the study period
- Number of transmission events of MDRO, detected by the current infection control procedures and by analysis of whole genome sequence data during the study period.

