13.2 Secondary outcome measures

The secondary outcome measures are:

- Risk factors for colonisation / infection with MDRO
- Outcome of patients colonised / infected with MDRO i.e. death or alive at discharge from ICU
- Cost-effectiveness of whole-genome sequencing versus standard epidemiological investigation / typing for suspected outbreaks of infection

14 Storage and analysis of samples

Study samples will be analysed and stored in the research laboratory in the Department of Medicine at Addenbrooke's Hospital.

The original screening specimens (swabs, urine, stool, respiratory samples) will be stored at $-80^{\circ}C$ +/- $10^{\circ}C$ in secure freezers. Positive culture isolates will also be stored at $-80^{\circ}C$ +/- $10^{\circ}C$ in secure freezers.

DNA extracts will be transferred in batches from the Department of Medicine research laboratory to the Wellcome Trust Sanger Institute for library preparation and bacterial whole-genome sequencing on a high-throughput sequencing platform.

15 Data analysis

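### The closing screen is defined only for ICU discharge, and nothing says what is sampled at death, so late acquisition is probably under-detected in patients who die and mortality in colonised patients understated

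*Protocol*

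**What the plan says.** Every participant has a baseline screen. Section 11.2.1: "Participants will be screened for MDRO on admission to the John Farman Intensive Care Unit". Section 11.3.1 adds the follow-up screens: "Participants will be screened for MDRO on discharge from ICU", plus weekly ones when the stay reaches 7 days. Section 11.5.1 repeats this ("Screening specimens will be collected on admission, on discharge, and weekly in patients admitted for ≥7 days according the following schedule"), and its table has columns for admission, discharge and weekly follow-up only. Section 11.4 ends participation at ICU discharge and does not mention death.

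A second route exists. Sections 11.2.2, 11.3.2 and 11.5.2 retrieve target organisms from diagnostic specimens, but those specimens are taken only when clinically needed.

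The results of these samples define two outcomes. The first primary outcome in section 13.1 is "Number of patients colonised with MDRO during the study period". A secondary outcome in section 13.2 is "Outcome of patients colonised / infected with MDRO i.e. death or alive at discharge from ICU".

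On length of stay in January 2015, section 9.4 gives a mean of 7.19 days (SD 8.94) and says "the median was 3.4 days (range 0.2 to 47.2 days").

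**The concern.** The exit screen is tied to one level of the outcome it is later set against. In a patient who leaves alive, acquisition can be seen up to the last day. In a patient who dies, it can be seen by scheduled screening only up to the last weekly screen, or only at admission if death comes before day 7. An acquisition in the gap is missed unless a diagnostic specimen happens to find it, and the patient is counted as not colonised.

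Two things follow. The proportion dying among colonised patients loses deaths from its numerator, which matters even if the figure is only described. Any comparison with non-colonised patients is pulled towards colonisation appearing harmless or protective. The same gap slightly lowers the primary colonisation count, although section 20.1 says the study depends on complete data capture.

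**Working it through.** **Planned number.** Section 15.1 gives 1100 to 1200 admissions a year. 1200 × 6/12 = 600 reproduces the plan; 1100 × 6/12 = 550. The counts below use 600. The protocol gives no ICU mortality, carriage or acquisition rate, so those are assumptions.

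**How many stays have no weekly screen.** A median of 3.4 days means that at least half of stays are under 7 days. Fitted distributions give:
- gamma with mean 7.19 and SD 8.94: shape (7.19/8.94)² = 0.647, 65% under 7 days (fitted median 4.0);
- lognormal with the same mean and SD: 68% (fitted median 4.5);
- lognormal with mean 7.19 and median 3.4: 72% (fitted SD 13.4).

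None matches all three stated figures. A patient who dies in such a stay has only the admission screen.

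**Simulation with no true effect.** Stays are gamma or lognormal, matched to the mean and SD. Admission carriage is 10% and always found. Acquisition is exponential at 1, 2 or 4% per day. ICU mortality is 15%, independent of colonisation and stay. In survivors every acquisition is found by discharge. In deaths it is found only if it precedes the last multiple of 7 days in the stay. The true odds ratio is 1.

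- No diagnostic detection: odds ratio about 0.61 (lognormal, 4% per day) to 0.85 (gamma, 1% per day).
- Diagnostic specimens find 30% of the missed acquisitions: about 0.72 to 0.90.
- Patients missed: about 1 to 8 of 600.

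**One case by hand** (gamma, 2% per day).
1. Admission carriers: 0.10 × 600 = 60. Acquirers from the simulation: about 66. Truly colonised: 126.
2. Missed acquirers: 4.93 per 600 at 20% mortality, hence 4.93 × 15/20 = 3.7 at 15%. All of them died.
3. Colonised as recorded: 126 − 3.7 = 122.3. Deaths among them: 0.15 × 126 − 3.7 = 15.2, or 12.4%.
4. The rest: 474 + 3.7 = 477.7. Deaths among them: 0.15 × 474 + 3.7 = 74.8, or 15.7%.
5. Odds ratio: (15.2/107.1) / (74.8/402.9) = 0.76.

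**Wider ranges.** With mortality 10–30%, carriage 5–20% and acquisition 1–3% per day (gamma), the mortality ratio is 0.68–0.93 with no diagnostic detection and 0.77–0.95 when diagnostic specimens find 30% of acquisitions. About 1 to 11 of 600 patients are missed.

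**With a true effect.** For a true mortality ratio of 1.5 (15% baseline mortality, 10% carriage, 2% per day), the observed ratio is 1.18, 1.27 or 1.37 when diagnostic specimens find 0, 30 or 60% of acquisitions.

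**Check of the remedy.** When everyone is classified by the same rule, without discharge screens, the simulated odds ratio returns to 0.99–1.01. This check assumes that death is unrelated to length of stay. It therefore cannot show the separate problem that a weekly positive requires a stay of at least 7 days.

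**The case against.** *Discharge may include death.* Section 13.2 can be read as treating death as one status at discharge. Sections 11.2.3, 11.3.3 and 11.4 tie closing data collection and the end of participation to discharge alone, which would leave deaths with neither if discharge excluded them. This is a fair reading, and it is why the text needs clarifying. But no section states it, and section 13.2 equally reads as setting death against leaving alive.

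*Patients who die are screened.* A reader might infer that they get no screen at all. The protocol does not support that: admission and weekly screens apply to them, and admission carriage is ascertained alike in both groups. Only acquisition after the last scheduled screen is at issue.

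*Diagnostic isolates fill the gap.* They do so in part, and section 13.2 covers infected as well as colonised patients. But the sampling is driven by clinical need and is not a systematic substitute.

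*No comparison is specified.* Section 13.2 describes colonised or infected patients, and the univariate and multivariate work in section 15.1 concerns risk factors for carriage and infection. This stands: the odds ratios above show what a comparison would yield, not a planned analysis. The descriptive mortality figure is still affected.

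*The direction is not certain.* This also stands. In one set of runs (20% mortality, 10% carriage, 2% per day) the ratio rose to 1.02–1.04, when survivors' discharge screens were only 50–60% complete and diagnostic specimens found 60–80% of acquisitions in patients who died.

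**Conclusion.** The gap is real under the schedule as written: the closing screen depends on the outcome, and the protocol is silent on sampling at death. The probable effect is to understate mortality in colonised patients, with an odds ratio of about 0.61–0.85 where the truth is 1, or 0.72–0.90 with 30% diagnostic detection. These figures rest on assumed mortality, carriage and acquisition rates, complete discharge screening in survivors, full test sensitivity and fitted lengths of stay.

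A reader might infer a much larger bias. Comparing acquirers alone with everyone else, with no admission carriers and no diagnostic detection, gives odds ratios of 0.47–0.62. That is not the protocol's group: section 13.2 takes all colonised or infected patients, and carriers found on admission dilute the error. Nor do the documents show that colonised patients will look safer; that is the expected direction only.

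The outcome is secondary and few patients are affected. The point should be corrected, but it does not threaten the study's main counts.

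**What to change.** In sections 13.2 and 15.1:

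1. State whether *discharge* includes death, and make sections 11.3.1, 11.4 and 11.5.1 agree with that.
2. For ICU death, make carriage on the admission screen the main exposure. It is ascertained in the same way whatever the outcome.
3. As a secondary analysis, treat acquisition found on weekly screens as a time-dependent exposure, because a fixed label would depend on having stayed at least 7 days. Leave out positives seen only at discharge, for survivors and deaths alike. Report detections from diagnostic isolates separately.
4. Keep discharge screens for the colonisation and transmission counts in section 13.1.
5. Report how many patients died with no screen after admission.

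The cost is wording and analysis only, with no new specimens. The downside is that acquisitions seen only at discharge do not contribute to this one outcome, so a patient may count as colonised under section 13.1 but not as exposed in this analysis. The report should say so.

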11.3.2 Diagnostic specimens

Diagnostic specimens will be collected as clinically indicated and processed in the diagnostic microbiology laboratory at Addenbrooke's hospital according to routine clinical practice.

Samples that are positive for the target organisms will be identified by the laboratory information system and retrieved daily on weekdays from the diagnostic microbiology laboratory, for further processing as detailed above.

11.3.3 Clinical data collection

Clinical and laboratory data will be collected on each patient by a research nurse who is part of the ICU clinical care team and entered into a case record form.

Clinical data collection will be performed on admission to ICU, on discharge from ICU and weekly during the ICU admission if the duration of admission is \geq 7 days.

Data will be entered into a secure electronic database located on the Addenbrooke's hospital server. Data will be anonymised as soon as it is practical to do so.

Cost data for microbiological tests, antibiotic costs and microbial whole-genome sequencing will be obtained from the diagnostic laboratory, the pharmacy

department at Addenbrooke's hospital, and from the Wellcome Trust Sanger Institute.

11.4 End of Study Participation

Subjects will cease to participate in the study when they are discharged from the John Farman Intensive Care Unit.

11.5 Sampling schedule

11.5.1 Clinical data collection and screening for MDRO (research specimens) Screening specimens will be collected on admission, on discharge, and weekly in patients admitted for ≥7 days according the following schedule:

Study specimens	Admission	Discharge	Follow-up (weekly)
Clinical data collection	\checkmark	\checkmark	\checkmark
Stool sample / rectal swab*	\checkmark	\checkmark	\checkmark
Urine	\checkmark	\checkmark	\checkmark
Sputum or tracheal aspirate	\checkmark	\checkmark	\checkmark
Wound swab (if applicable)	\checkmark	\checkmark	\checkmark

*A rectal swab will only be collected if a stool sample is unavailable. This is standard clinical practice for screening for carbapenem-resistant organisms, as recommended by the Public Health England guidelines.

Specimens will be sent to the research laboratory in the Department of Medicine for processing Monday to Friday.

Samples that are collected at the weekend will be stored at 4° C in a refrigerator on the ICU and processed the following Monday.

11.5.2 Diagnostic specimens

Diagnostic specimens will be taken as clinically indicated and sent to the diagnostic microbiology laboratory for processing. The results of these investigations will be available to the clinical staff on ICU, and any infections will be managed according to routine clinical practice.

If any target organisms are cultured in sterile site specimens (e.g. blood cultures, cerebrospinal fluid, pleural fluid, ascitic fluid, joint aspirate) they will be identified via the laboratory database and collected from the diagnostic laboratory on weekdays. This will enable us to include samples / isolates that are not captured by the regular screening procedures described in section 9.5.1 above.

11.5.3 Environmental sampling

In order to determine the prevalence of the target organisms in the ICU environment as a possible source of infection we will perform environmental sampling prior to study commencement and at monthly intervals throughout the study.

Environmental samples will be collected using swabs from the following areas of the intensive care unit:

- Door handles of patient rooms
- Taps in patient rooms or adjacent to patient beds
- Bed rails
- Ventilation equipment
- Patient tables
- Computer keyboards

Environmental samples will be sent to the research laboratory in the Department of Medicine for processing Monday to Friday.

Samples that are collected at the weekend will be stored at 4° C in a refrigerator on the ICU and processed the following Monday.

12 Assessment of Safety

This is a prospective observational cohort surveillance study of MDRO in the John Farman Intensive Care Unit.

All participants will receive routine clinical care, including antimicrobial therapy for infections, if clinically indicated.

There are no study-specific interventions or treatments and therefore no need for study-specific safety assessments.

If the patient develops an adverse event then this will be managed according to routine clinical care and reported through standard NHS clinical governance and complaints procedures.

13 Outcome measures

13.1 Primary outcome measures

The primary outcome measures are:

- Number of patients colonised with MDRO during the study period
- Number of patients with clinical evidence of infection with MDRO during the study period
- Number of transmission events of MDRO, detected by the current infection control procedures and by analysis of whole genome sequence data during the study period.

13.2 Secondary outcome measures

The secondary outcome measures are:

- Risk factors for colonisation / infection with MDRO
- Outcome of patients colonised / infected with MDRO i.e. death or alive at discharge from ICU
- Cost-effectiveness of whole-genome sequencing versus standard epidemiological investigation / typing for suspected outbreaks of infection

14 Storage and analysis of samples

Study samples will be analysed and stored in the research laboratory in the Department of Medicine at Addenbrooke's Hospital.

The original screening specimens (swabs, urine, stool, respiratory samples) will be stored at $-80^{\circ}C$ +/- $10^{\circ}C$ in secure freezers. Positive culture isolates will also be stored at $-80^{\circ}C$ +/- $10^{\circ}C$ in secure freezers.

DNA extracts will be transferred in batches from the Department of Medicine research laboratory to the Wellcome Trust Sanger Institute for library preparation and bacterial whole-genome sequencing on a high-throughput sequencing platform.

15 Data analysis

